## 5.0 Required Studies and Schedule:

**Eligibility Determination:** Subjects will be seen at the RPCI screening clinic and their eligibility for the pilot study will be determined. If they agree to participate, they will be asked to sign the IRB approved informed consent. At this time (Month 0) they will have blood, collected, complete the study questionnaires. Vitamin D status will be measured at baseline. A medical history, a complete smoking exposure history as per standard clinic routine, enrollment into the DBBR and vitamin/supplement use information as per EMR medication record will also be completed at this time.

**Month 0, Day 1** Subjects will receive their 3-month supply of capsules in a labeled blister pack at this time from the study nurse. At this time the PK/PD studies will be initiated.

### Pharmacokinetics:

**Pharmacokinetics Sampling Times:** PK samples will be collected at pre-dose and at hours 0.5, 1, 3, 5, and post-dose 24 hours on Day 2. Samples of blood (4 ml) will be collected in EDTA tubes centrifuged at 4° C and serum is stored frozen at -80° C until analysis by RIA (see attached protocol for analytical details). Derivation of PK parameters and modeling is described below. Serum Chemistry for 25-D3 levels will be measured at baseline. The measurement of the calcitriol levels will be performed in the PK/PD facility at RPCI. One aliquot of buffy coat (lymphocytes) will be collected from these samples and stored at -80C. These aliquots will be sent to the Prevention Laboratory and stored until requested by [name] for pharmacogenomics analysis.

Blood samples will be made available through DBBR Vitamin D (BIOKIT IV) (RPCI approved protocol I 03103), after the patient has been consented for DBBR. All samples and associated data from DBBR will be stripped of PHI and provided with a new study ID prior to receipt. Per protocol, the DBBR will maintain the key between the participant's PHI and study ID. Only the DBBR staff (Principal Investigator and Data Manager) associated with operating the bank have access to this link. The key will never be given to the investigator of this study.

Blood samples will be collected and stored for future studies by the RPCI Data Bank and Bio Repository (DBBR), per Standard Operating Procedures for vitamin D trial banking. The DBBR is a shared resource (RPCI protocol I 03103), where participants are consented to donate blood for research (prior to and following treatments), to complete an epidemiologic questionnaire, and to give permission to have their blood specimens linked to the questionnaire and clinical data including diagnosis and laboratory test results for research. Collected biospecimens and/or data are provided to investigators with RPCI IRB approved research protocols.

Other samples will be made available through Lung Cancer Screening Program (EDR 11003). The samples and associated data from Lung Cancer Screening Program will be stripped of PHI and provided with a new study ID prior to receipt. Lung Cancer Screening Program will maintain the key between the participant's PHI and study ID. Only the Lung Cancer Screening Program staff (Principal Investigator and Data Manager) associated with operating the bank have access to this link.

I 90206 Amendment # 18

Once the molecular analysis is finished, the data from molecular analysis and information from DBBR will be linked to Lung Cancer Screening Program database by staff members in Lung Cancer Screening Program.

**Weekly Blood Evaluations:** After the first dose on calcitriol is taken on Day 1, and the PK study has been done, the patients will return for blood collection on Day 2 (24 hours after the first dose) and on the same day of the week after the pill is taken (Day 16) for the first month of treatment (encompassing two doses) and then monthly for the remainder of the 3-month study period. The patient will not be seen in the clinic but will go directly to phlebotomy. Blood collection will then be done at the end of Months 2 and 3, when the patient is seen by the clinic nurse for toxicity assessment (Weekly blood evaluations may be collected at participating sites).

**Phone Calls for Pill Reminders and Toxicity Monitoring:** The CRC will call each patient the day before the pill is due to be taken and on the day after the calcitriol is taken, to ask about all potential AE and SAE reactions. If the patient has started taking the treatment on Monday, the nurse may call the patient on Friday before. During these phone calls, the CRC will also assess compliance to the treatment schedule.

**Study Clinical Visits and Closeout Visit (Months 1, 2 and 3):** Each month that patient will come into the clinic at RPCI (or participating sites) and have a toxicity evaluation performed by the clinic nurse. At the end of the three month period, patients will return to the clinic at RPCI (or participating site) and have a final blood draw and toxicity evaluation. The blood collected will be immediately processed to yield the samples for calcium. All remaining samples will be archived at -86 degrees for future analyses. At each clinical visit, the clinic nurse will interview subjects for the onset of new illnesses or hospitalizations, changes in smoking, vitamin supplement use, and potential symptoms related to calcitriol toxicity as per standard clinic routine. The bronchoscopy will be done after the cessation of the intervention and according to the patient's routine follow-up schedule.

**Procedures for Toxicity Monitoring and Reporting:** The study nurse will assess potential toxicities during each phone call. If a subject reports changes in any of these symptoms, they will be documented as an AE and graded according to CTCAE 4.0. If the patient reports an AE of  $\geq 3$  grade, it will be reported to the PI or the treating physician to determine if they need to be evaluated at Roswell Park. The complete toxicity information will be reported to the medical director, [name], at the time of continuing review. Reports regarding toxicity, patient safety, and study progress will be submitted to the RPCI Institutional Review Board (IRB), FDA and to the NCI at the end of the study. The risks and side effects that have been reported to be associated with calcitriol include:

Likely Side Effects: those that may occur in approximately 10% - 30% of persons who receive this drug.	

• Most of the side effects described with calcitriol are related to elevations of calcium referred to as hypercalcemia (33%).

• Side effects related to high calcium can occur which include, kidney and bladder stones, weakness, dehydration, constipation, muscle aches, nausea, vomiting.

---	---

Unlikely Side Effects: those that occur in approximately 5% to 9% of persons who receive this drug.
	

• Cardiac arrhythmia (disorders of the regular rhythmic beating of the heart), high or low blood pressure.

• Headache, irritability, seizure (rare), somnolence (sleepiness), psychosis (inability to think clearly).

• Pruritus (itching of the skin), erythema (reddening of skin), multiforme (allergic reaction that occurs in response to medications).

• Hypermagnesemia (excess magnesium), hyperphosphatemia (high level of phosphate in blood), polydipsia (excessive thirst).

• Anorexia, constipation, metallic taste, nausea, pancreatitis, vomiting, xerostomia (dry mouth).

• Elevated liver function tests

• Bone pain, myalgia (muscle pain), dystrophy (weakness of muscles), soft tissue calcification

• Conjunctivitis (pink eye), photophobia (sensitivity to light)

• Polyuria (increased urination)


Rare but Serious Side Effects: Those that occur in less than 1% of persons who receive this drug/undergo this procedure.
	

• Rarely, the calcium levels become too high (rarely) then confusion, irregular heartbeats, inflammation of the pancreas and coma can occur.

Unknown Side Effects: Those for which there is no information.
	

• There is no information on the effects of active smoking when taking calcitriol.

**Toxicity Monitoring:** Any grade 3 or worse toxicity regardless of attribution or a grade 2 toxicity that persists for more than 2 weeks, will be reported to the FDA and the patient will be removed from the study. In addition, all Grade 1 and short-term 2 toxicities will be reported to the FDA at the end of the study, regardless of attribution.

**Removal from Study:** Patients will be removed from study for any of the following reasons:

1. Any grade  $\geq 3$  related to study drug.
2. A grade 2 that persists for more than two weeks.
3. Interim development of new malignancy (lung or extra pulmonary).
4. Withdrawal of consent.

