Eligibility Interview	X																						
Informed Consent	X																						
Complete Physical Exam	X																						
Medical History Update	X																						
Toxicity Evaluation (Nurse)	X	X	X				X															X	X
Spirometry and FEV1	X																						
Renal Ultrasound	X																						
24 hour urine collection (2)	X																						
Assessment of Supplement Use	X																						
Chemistry Panel (3) and ionized calcium	X		X			X	X															X	X
Hematology Panel (3)	X		X			X	X															X	X
25-OH vitamin D	X																						X
Dose 45 mcg Calcitriol (QOW)		X			X			X									X		X		X		
PK Samples for Calcitriol (4)		X	X																				
AF Bronchoscopy	X																						X

Phone call dose reminder				X		X			X		X		X			
Phone call toxicity check						X	X	X	X	X	X	X	X	X	X	
Blood for future studies ( 5)	X	After 24-48 hours and every 3 months while on treatment if the patient signs the DBBR consent														

1. Follow up labs will be done only for patients with toxicities at the time of cessation of the treatment.

2. 24 hour urine will be collected for the measurement of creatinine and calcium concentration.

3. **Chemistry Panel:** Chloride, CO2, Potassium , sodium, urea nitrogen, Glucose, Calcium, ionized Serum Calcium, Creatinine, Total Protein, Albumin, Aspartate aminotransferase, Alanine aminotransferase, osmolality serum, Anion gap, BUN/Creatinine ratio, Pregnancy test within 1 wk of enrollment (screening only).

**Hematology:** CBC will be monitored every other week in the first month then monthly until the end of the intervention.

The blood collection will occur on the day after the pills are taken. Vitamin D levels (25-OH-Vitamin D) will be drawn twice.

4. PK/PD sampling: Blood will be taken for PK/PD at the following time points, predose, .5, 1, 3, 5 and 24 (day 2) hours post dose.

5. Blood samples will be drawn before treatment, 24-48 hours following initiation of treatment and every three months during treatment alongside clinical blood draws, and frozen for future correlative studies. Samples will be drawn in phlebotomy and sent to the RPCI Data Bank and Bio Repository for storage per DBBR Standard Operating Procedures for Vitamin D Trial banking participants

I 90206 Amendment # 18

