The labeled calcitriol capsules will be sent by courier to Roswell Park and delivered to the Investigational Drug Service (IDS) where the capsules will be held until the patient returns to the clinic to start the trial. The PK/PD studies will start at time 0 and then the patient will take the first capsule. The PK/PD studies will be carried out as described in following sections.

**Calcitriol Formulation and Dispensing:** In each size 3 opaque capsule there will be 200 microliters of solution containing:

- 45 mcg Calcitriol
- 0.1% of each BHT and BHA (Concentration PCCA uses in their product 12000 nanograms/ml) in Almond oil as the vehicle.

The blister packs are heat sealed and placed in an amber ziplock bag to protect the capsules from sunlight.

Storage: After the completion of the PK/PD studies on Day 0, the patients take the blister pack home and store it in the refrigerator until two weeks later when they take another capsule.

Stability: Shelf life surveillance studies of formulated capsules are ongoing. Current data indicates calcitriol is stable for at least 5 years at room temperature when protected from light.

Method of Administration: Capsules should be taken once every other week. Subjects should take calcitriol on an empty stomach (at least one hour before or two hours after meals) and drink approximately 4 cups of liquids in addition to their usual intake in the day of taking the pill and for the next two days.

**8. Specimen and Data Collection and Processing:** A complete smoking history will be collected as per the clinic routine.

**Measurement of Plasma Vitamin D:** Blood samples for calcitriol determination will be sent to the PK/PD facility at RPCI for analysis. Patients will be coming into to have blood draw the day after taking the tablet. Plasma samples will be separated from 4 ml of blood collected in EDTA tubes for plasma calcitriol measurements. The samples will be centrifuged at 1400rpm at 4°C for 10 minutes and stored at -80°C until assayed.

I 90206 Amendment # 18

[figure not shown]

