## 11.1 Reporting Adverse Events

**Table 1 Guidelines for Routine Adverse Event Reporting for Pilot, Phase 2, and Phase 3 Studies (Regardless of Expectedness)**

Attribution	Grade 1	Grade 2	Grade 3	Grade 4
Unrelated			X	X
Unlikely			X	X
Possible	X	X	X	X
Probable	X	X	X	X
Definite	X	X	X	X

Routine AEs occurring between the start date of intervention until 30 days after the last intervention or until the event has resolved, the study participant is lost to follow-up, the start of a new treatment, or until the study investigator assesses the event(s) as stable or irreversible, will be reported. New information will be reported after it is received.

As requested by the FDA, final reporting of AEs will include all AEs regardless of attribution.

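### After month 1, required bloods are about 28 days apart with no timed retest, so an asymptomatic Grade 2 laboratory value cannot be classed against the two-week criterion unless it is still Grade 2 a month later

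*Combined protocol and SAP*

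**What the plan says.** All references are to the combined protocol and SAP.

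- **Endpoint and limits.** The Abstract (Primary Endpoints) and Section 12 count Grade 3-4 toxicities and Grade 2 toxicities that outlast two weeks. Section 12 allows a stop at 1 or fewer of 20 and rejects the 10% null at 8 or more of 40.
- **Removal.** The list in Section 5.0 includes "A grade 2 that persists for more than two weeks". Section 11.2.3 repeats it.
- **Required bloods.** Section 5.0 (Weekly Blood Evaluations) sets draws on Days 2 and 16, then monthly: "Blood collection will then be done at the end of Months 2 and 3, when the patient is seen by the clinic nurse". The flow chart also appears to mark chemistry on Day 28. More frequent sampling is optional: "Weekly blood evaluations may be collected at participating sites".
- **Follow-up labs.** Flow chart footnote 1: "Follow up labs will be done only for patients with toxicities at the time of cessation of the treatment". No day is given.
- **Tracking.** Section 11.1 covers "Routine AEs occurring between the start date of intervention until 30 days after the last intervention or until the event has resolved", with no retest date.
- **Draw day relative to dose.** Section 5.0 says end of month. Footnote 3 says "The blood collection will occur on the day after the pills are taken", and Section 8 says "Patients will be coming into to have blood draw the day after taking the tablet".
- **Between draws.** Phone calls around each dose ask about symptoms (Section 5.0).

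**The concern.** A 14-day criterion is being read from draws 28 days apart. The gap falls on the toxicity that matters most. Section 9 names hypercalcemia as dose limiting and describes Grade 2 cases as transient and, in the Phase 1 study, asymptomatic. Phone calls would not find such a case or show when it ended.

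Two things are at stake. Whether a detected Grade 2 value enters the primary count would rest on judgment, and one patient separates 1 from 2 at the interim and 7 from 8 at the end. The removal rule is a safety rule, and no required result is available when it could first apply.

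**Working it through.** The plan attaches no figure to this point, so there is none to reproduce. The stated power is not an input.

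**1. Inputs.** Six doses, one every two weeks (Section 7): Days 1, 15, 29, 43, 57, 71. Required draws: Days 2, 16 and 28, then 56 and 84, taking the end of a month as Day 28 of a 28-day month (assumption). The gaps are 14, 12, 28 and 28 days.

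**2. Bounds on duration.** If the value is below Grade 2 at the next draw, duration is more than 0 and less than (next draw minus last draw below Grade 2).

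| First Grade 2 | Last below Grade 2 | Next draw | Upper bound if next is below Grade 2 | Span if next is still Grade 2 |
|---|---|---|---|---|
| Day 28 | Day 16 | Day 56 | 56 - 16 = 40 days | 28 days |
| Day 56 | Day 28 | Day 84 | 84 - 28 = 56 days | 28 days |

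Both ranges contain 14 days, so neither case can be classed. If the next value is still Grade 2, the readings span 28 days and the event would ordinarily be called persistent. That takes it as continuous across two intervening doses, for which the plan has no rule.

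**3. Persistent episodes that can never be confirmed.** An episode starting after Day 16 and lasting 15 to under 28 days covers at most one of Days 28, 56 and 84. It exceeds two weeks, yet never gives two Grade 2 readings more than 14 days apart.

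**4. Timing of removal, counted from the first Grade 2 reading.**
- *End-of-month draw.* Day 28 to the Day 43 dose is 15 days, and the next required result is Day 56. Day 56 to the Day 71 dose is 15 days, and the next required result is Day 84. The Day 29 and Day 57 doses come one day after the reading, so the rule does not yet bite.
- *Day-after-dose draw.* The next two doses fall 13 and 27 days later, and a draw 28 days on follows both. The rule cannot apply at 13 days; it could at 27, with no required result in hand.

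**5. What a repeat at +15 days can and cannot do.** Assume onset uniform over Days 16-56 (40 days) and true length L between 17 and 25 days. The episode is seen at Day 28 for 12 days of onset and at Day 56 for L days, so the share seen is (12 + L)/40. It is still Grade 2 at +15 days if onset fell in the last L - 15 days before either draw, a share of 2(L - 15)/40.

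| L (days) | Seen | Still Grade 2 at +15 | Share of those seen |
|---|---|---|---|
| 17 | 29/40 = 72.5% | 4/40 = 10% | 14% |
| 21 | 33/40 = 82.5% | 12/40 = 30% | 36% |
| 25 | 37/40 = 92.5% | 20/40 = 50% | 54% |

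The repeat raises the share confirmed as persistent from 0% to 30% at 21 days and from 0% to 50% at 25 days. Calling all the rest short would undercount persistent events, because onset before the first positive draw is unobserved.

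**The case against.** The best defence is that the plan does not prevent retesting. Persistence beyond two weeks triggers removal and an FDA report, so an investigator holding a Grade 2 value has reason to recheck. Section 9 lists serum calcium monitoring as risk minimization, Section 11.1 follows events to resolution, and participating sites may draw weekly. This stands as far as it goes: what is missing is a required interval, not the ability to retest. But a primary endpoint should not depend on optional tests.

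Three stronger readings are tempting and are not supported.

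- *That such values can never be classed.* A value still Grade 2 at the next monthly draw ordinarily would be, and optional or unscheduled bloods could settle others.
- *That particular doses, such as Days 43 and 71, would be given against the removal rule.* Those days depend on an end-of-month draw, while footnote 3 and Section 8 point to the day after a dose. The chart columns for months 2 and 3 are not legible in the copy reviewed and may settle it. Only the lateness of the next required result holds on both readings.
- *That the decision limits are shifted by a known amount or in a known direction.* The nearest rate, 3 of 37 in Section 9, comes from MDS patients on weekly DN-101, another formulation. It counts transient events, so it says nothing about how often persistent ones occur, and nothing gives the share that would be misclassified.

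A monthly laboratory schedule is also a legitimate design choice. Grade 3-4 events and symptomatic Grade 2 events found by phone are unaffected. Reporting of short Grade 2 events is also covered: "all Grade 1 and short-term 2 toxicities will be reported to the FDA at the end of the study".

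**Conclusion.** The concern holds in a limited form. For an asymptomatic Grade 2 laboratory value first seen at a monthly draw, required data cannot place it above or below two weeks unless it is still Grade 2 at the next monthly draw. That result arrives about 28 days later, too late to apply the removal rule on time. The possible durations run up to 40 or 56 days, and episodes of 15 to under 28 days starting after Day 16 cannot be confirmed at all.

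This rests on the Section 5.0 text for the draw schedule, on 28-day months, and on no optional or unscheduled test being done. No net bias is shown, and the effect on the 1-of-20 and 8-of-40 limits cannot be sized from the documents. The change is still worth making: it bears on the primary endpoint and a patient-safety rule, and it costs little.

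**What to change.** 1. **Retest.** In Section 5.0 (Weekly Blood Evaluations), after any Grade 2 laboratory value during treatment, require a repeat of the affected test (ionized calcium for hypercalcemia) before the next dose. If still Grade 2, repeat about 15 days after the first value and remove the patient if it is Grade 2 then. Apply the same timing to the end-of-treatment labs in flow chart footnote 1.
2. **Draw day.** State one draw day relative to dose for months 2 and 3. A day-after-dose draw leaves 13 days for the first repeat; an end-of-month draw leaves one. With day-after-dose draws the 15-day repeat falls two days after the next dose is due, so say whether that dose waits.
3. **Classification.** Bound duration from the last value below Grade 2 before the episode to the first one after it. Count as persistent if the Grade 2 readings span more than 14 days, and as short if the outer bound is 14 days or less. Otherwise report the primary count both ways against the 1-of-20 and 8-of-40 limits.

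**Cost.** Protocol wording, and up to two extra draws per Grade 2 laboratory value in affected patients only. If the 3-of-37 rate applied, that is 40 x 3/37 = 3.2 patients for hypercalcemia, or 1.6 if every-other-week dosing halved it; both are assumptions. Other Grade 2 laboratory values would add to this at a rate the documents do not give.

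**Limits.** Some episodes stay indeterminate because onset is unobserved. With end-of-month draws, a Day 28 value that is below Grade 2 on Day 29 can be called short (29 - 16 = 13 days). A Day 56 value cannot, because the last lower reading was 28 days before. The two-way count may therefore straddle a limit. Episodes wholly between draws are still missed.

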## 6. STRATIFICATION AND RANDOMIZATION

This is a single armed study and there will not be any randomization.

## 7. TREATMENT PLAN

**Informed consent:** All patients prior to enrollment in this study will sign an Informed Consent in conformity to Federal and Institutional guidelines.

I 90206 Amendment # 18

**Calcitriol Administration:** The subjects will receive 45mcg /QOW of oral calcitriol capsules one day every other week. Subjects will take one capsule QOW for 3 months, for a total of 6 capsules. Subjects will be supplied with 3 months' worth of capsules (6 capsules) dispensed by the UB pharmacy.

When the patient has signed the informed consent, eligibility confirmed they will be scheduled to take their first dose and have PK/PD studies. A fax will be sent to [name], RPh at the Suny at Buffalo, Buffalo School of Pharmacy. . This fax will include: A completed prescription for the calcitriol (the original will be sent to [name] by courier that week) and the date of the patient's next scheduled visit.

Her complete contact information is:

[name], RPh, MS  
SUNY at Buffalo, Buffalo School of Pharmacy  
School of Pharmacy and Pharmaceutical Sciences  
[name]  
South Campus  
[name]  
[contact]  
[contact]

Upon receipt of the fax, [name] will label 6 individual blister packs for the calcitriol capsule 45mcg/cap. The label on each blister pack will include the following information:

SUNY at Buffalo, Buffalo School of Pharmacy  
New Drug Investigational use  
Calcitriol 45 mcg/capsule  
[name] RPh [name] Date

The 6 blister packs will be placed in an amber zip-lock bag and labeled with patient specific information. The label on each ziplock bag will include the following information:

SUNY at Buffalo, Buffalo School of Pharmacy  
Research Pharmacy  
[name] [contact] RPh: [name]

Subject's Name	Subject #	Fill Date
Subject's Address		

Take one capsule on an empty stomach (at least one hour before or two hours after meals) and drink approximately 4 cups of liquids in addition to your usual intake in the day of taking the pill and for the next two days as directed by project protocol.

Quantity: 6 blister paks  
Calcitriol 45mcg/capsule

I 90206 Amendment # 18

In case of an emergency, please contact Roswell Park Cancer Institute [contact]) and ask to speak to the Department of Medicine physician on call.

"Caution: New Drug--Limited by Federal (or United States) law to investigational use."

An auxiliary label "Keep in Refrigerator Do not Freeze" will be placed on the amber ziplock bag.

The labeled calcitriol capsules will be sent by courier to Roswell Park and delivered to the Investigational Drug Service (IDS) where the capsules will be held until the patient returns to the clinic to start the trial. The PK/PD studies will start at time 0 and then the patient will take the first capsule. The PK/PD studies will be carried out as described in following sections.

**Calcitriol Formulation and Dispensing:** In each size 3 opaque capsule there will be 200 microliters of solution containing:

- 45 mcg Calcitriol
- 0.1% of each BHT and BHA (Concentration PCCA uses in their product 12000 nanograms/ml) in Almond oil as the vehicle.

The blister packs are heat sealed and placed in an amber ziplock bag to protect the capsules from sunlight.

Storage: After the completion of the PK/PD studies on Day 0, the patients take the blister pack home and store it in the refrigerator until two weeks later when they take another capsule.

Stability: Shelf life surveillance studies of formulated capsules are ongoing. Current data indicates calcitriol is stable for at least 5 years at room temperature when protected from light.

Method of Administration: Capsules should be taken once every other week. Subjects should take calcitriol on an empty stomach (at least one hour before or two hours after meals) and drink approximately 4 cups of liquids in addition to their usual intake in the day of taking the pill and for the next two days.

**8. Specimen and Data Collection and Processing:** A complete smoking history will be collected as per the clinic routine.

**Measurement of Plasma Vitamin D:** Blood samples for calcitriol determination will be sent to the PK/PD facility at RPCI for analysis. Patients will be coming into to have blood draw the day after taking the tablet. Plasma samples will be separated from 4 ml of blood collected in EDTA tubes for plasma calcitriol measurements. The samples will be centrifuged at 1400rpm at 4°C for 10 minutes and stored at -80°C until assayed.

I 90206 Amendment # 18

[figure not shown]
